## 5 Study Procedures

Care of patients follows standard procedures established by the local hospital. Blood samples will be taken according to the study design. At each blood sampling period, the study investigator will evaluate the suitable blood volume to be taken, based on body weight, health status and other guidelines from the hospitals.

Feeding regime follows the practice at the local NICU: mother's own milk is the first priority, followed by donor milk and infant formula. For each time of feeding, the following details are noted in the feeding CRF: time, type of feeding (mother's milk, donor milk, formula), feeding volume, gastric residual from previous feeding. For feeding intolerance, any interventions such as aspiration, decreased the amount of feeding or stop feeding are noted in the comments section of the CRF.

### 5.1 Diagnosis of chorioamnionitis, LOS and NEC

Once the patient is recruited, information about diagnosis of chorioamnionitis is collected and filled in the CRF. Clinical chorioamnionitis is defined in pregnant women with fever ( $\geq 38^{\circ}\text{C}$ ), high heart rate ( $\geq 100/\text{min}$  for mothers and  $\geq 160/\text{min}$  for fetuses), as well as when plasma CRP and blood leukocyte counts  $\geq 20 \text{ mg/L}$  and  $12,000 \text{ leukocytes/mm}^3$ . Histological chorioamnionitis is confirmed after histologic examination of the fetal membranes.

LOS is defined as sepsis occurring after 72 hours after birth. Clinical diagnosis of LOS is defined when the patient shows two or more of the following criteria: white blood cell count  $< 5 \times 10^9 \text{ cells/L}$  or  $> 20 \times 10^9 \text{ cells/L}$ , total platelet count  $< 100 \times 10^9 \text{ cells/L}$ , CRP  $> 10 \text{ mg/L}$ , procalcitonin  $> 2 \text{ ng/mL}$ . Culture-proven sepsis is defined as clinical sepsis with positive blood bacterial culture result.

Diagnosis of NEC is based on the conventional Bell system (IA, IB, IIA, IIB, IIIA and IIIB). Medical NEC is defined when an infant is diagnosed at stage IA to IIB. When an infants is classified with Bell stage III A or B (advanced NEC and bowel perforation), surgical interventions is required (surgical NEC).

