### 3 Study Design

#### 3.1 General Design

- This observational prospective cohort study includes 200 preterm infants, born < 32 weeks of gestation, at Neonatal Department, Bao'an Maternal and Child Health Hospital, Shenzhen, Guangdong, China.
- Patients, who fulfill inclusion criteria, will be recruited following the parental consent. The recruitment stops when the sample size reaches 200. Expected study duration: January 2017-June 2018.
- Patients will follow usual clinical procedures at the hospital. Patient groups will be categorized based on clinical records: infants born without and with clinical chorioamnionitis, infants without or with at least one episode of late-onset sepsis (LOS) and/or necrotizing enterocolitis (NEC).
- Enrollment and sampling are performed as indicated in the diagram below. Blood sampling is performed every week from birth until 4 weeks of age, or until discharge

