#### 3.2 Primary Study Endpoints

- Circulating markers in temporal postnatal blood samples associated with chorioamnionitis.

- Circulating markers in temporal postnatal blood samples associated with prognosis and/or diagnosis of neonatal LOS and/or NEC

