### **5.3 Sample selection, analysis and comparison**

At the end of the study, the selection of appropriate samples for analysis will be conducted by all investigators of the study. Samples included in the analysis are those collected from birth until the disease diagnosis or completion of 4 postnatal weeks. In case of clinical diagnosis of LOS and/or NEC before completion of 4 weeks, further routine sample collection after diagnosis is continued if feasible.

Temporal samples will be analyzed to perform three separate comparisons:

- Infants without versus with LOS and/or NEC
- Infants without versus with clinical/histological chorioamnionitis
- Infants with major or minor amount of mother's own milk during the first two weeks of life ( $\geq$  or < 50% of feeding times as complete mother's own milk).

Plasma proteomic study will be prioritized and will include as many samples as possible, followed by validation with absolute quantification of potential proteins using immune assays. The type of other -omic analysis for plasma (miRNA profiling) whole blood (transcriptomics or epigenetics) as well as sample size will be decided depending on the results of proteomic study.

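### Does the late-onset sepsis definition leave culture-positive infants without laboratory support unclassified, and so damage the marker analysis?

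*Protocol*

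**What the plan says.** Protocol 5.1 builds the late-onset sepsis (LOS) label in three steps. Timing comes first: "LOS is defined as sepsis occurring after 72 hours after birth". The working rule follows: "Clinical diagnosis of LOS is defined when the patient shows two or more of the following criteria", the four criteria being white cell count, platelets, CRP and procalcitonin. Then comes the sub-type: "Culture-proven sepsis is defined as clinical sepsis with positive blood bacterial culture result". A culture thus refines a clinical case and does not create one.

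Section 3.2 lists as a primary endpoint "Circulating markers in temporal postnatal blood samples associated with prognosis and/or diagnosis of neonatal LOS and/or NEC". Section 5.3 sets the comparison as "Infants without versus with LOS and/or NEC", and 6.2 repeats the split and adds a panel chosen by regression with ROC analysis. On the source of the grouping, 3.1 says "Patient groups will be categorized based on clinical records". On timing it says "Blood sampling is performed every week from birth until 4 weeks of age, or until discharge". Section 5.3 adds that "At the end of the study, the selection of appropriate samples for analysis will be conducted by all investigators of the study".

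Section 6.1 expects 200 infants, 20-30% of them with clinical LOS and/or NEC. The background (1.1) calls blood culture the gold standard, in inverted commas, and criticises it for missing cases and for being slow.

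**The concern.** Take an infant with a positive culture on day 10, one abnormal laboratory value and no NEC. Neither LOS definition is met, and no sentence names the class. If the infant counts as a control, a possibly infected child is used as the healthy comparison for sepsis markers, which pulls their apparent accuracy down. If the investigators may decide after the data are in, the ROC result would depend on that decision.

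The second worry is circularity. CRP and procalcitonin are two of the four criteria behind the label. Scored against it in blood from the diagnostic draw, they would look better than they are, and a new marker would look worse beside them. Both worries touch a primary endpoint.

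**Working it through.** **1. Does the text give a class?** The passages, side by side:

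- 5.1: LOS needs two or more criteria; a culture sub-types a case that already exists.
- 5.3 and 6.2: infants are split into with and without LOS and/or NEC, and there is no third group.
- 3.1 says where the grouping data come from. It is not a rival definition.
- The end-of-study selection in 5.3 concerns which samples to assay, not which class an infant belongs to.
- 1.1 faults culture for false negatives. Section 5.1 answers that fault by admitting culture-negative clinical sepsis as LOS. Nothing in 1.1 says that a positive culture alone must make a case.

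The literal result is a control. It is left implicit, but no passage contradicts it.

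**2. Group sizes.** The 200 is a feasibility figure, so there is no power calculation to reproduce. 200 × 0.20 = 40 and 200 × 0.30 = 60 cases, leaving 160 and 140 controls.

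**3. Yardstick.** Hanley-McNeil variance at an assumed AUC A = 0.80: [A(1−A) + (n₁−1)(Q₁−A²) + (n₀−1)(Q₂−A²)]/(n₁n₀), with Q₁ = A/(2−A) = 0.6667 and Q₂ = 2A²/(1+A) = 0.7111.

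- 40/160: (0.16 + 39×0.0267 + 159×0.0711)/6400 = 0.00195, SE 0.044.
- 60/140: (0.16 + 59×0.0267 + 139×0.0711)/8400 = 0.00138, SE 0.037.

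**4. Simple dilution.** If x of the true cases sit among the controls and share the cases' marker distribution, the observed AUC is A(1−f) + 0.5f, with f = x/controls. Assume A = 0.85.

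| True cases | x | f | Observed AUC |
|---|---|---|---|
| 40 | 2 | 2/162 = 0.012 | 0.846 |
| 40 | 5 | 5/165 = 0.030 | 0.839 |
| 40 | 10 | 10/170 = 0.059 | 0.829 |
| 60 | 2 | 2/142 = 0.014 | 0.845 |
| 60 | 5 | 5/145 = 0.034 | 0.838 |
| 60 | 10 | 10/150 = 0.067 | 0.827 |

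The loss is 0.004-0.023. Power for a difference of an assumed 0.5 SD is Φ(d(1−f)√(n₁n₀/200) − 1.96). With 40 cases it is 0.807 when none are misplaced, 0.782 with 2 and 0.661 with 10. With 60 cases it is 0.900, 0.886 and 0.815.

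**5. Simulation.** 400,000 infants per setting. Assumed:

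- 20% or 30% truly infected;
- each of four criteria 90% specific;
- infection shifts every marker by 0.8, 1.0, 1.5 or 2.0 SD, with correlation 0.2 or 0.4;
- culture positive in 30, 50 or 70% of infected infants.

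That makes 24 settings at each infection rate. Culture was taken as positive in 2% of uninfected infants, except that the hold-out gain also covers 0%. The marker studied is not part of the label, and NEC is left out.

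| Quantity | 20% infected | 30% infected |
|---|---|---|
| AUC gain from holding these infants out of the controls | 0.002-0.017 | 0.003-0.025 |
| Settings in which holding out is nearer the true AUC | 13 of 24 | 12 of 24 |
| AUC difference, control versus case | 0.010-0.059 | 0.002-0.061 |
| Such infants per 200 | 4-20 | 4-29 |
| Share of them uninfected | 14-76% | 9-65% |

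At 10% infected the hold-out gain is 0.001-0.009.

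**6. CRP and procalcitonin.** In the same draw that sets the label, at shifts of 0.8-1.5 SD, a defining marker with true AUC 0.71-0.86 reads 0.82-0.91. That is 0.05-0.11 above an equally accurate outside marker; at 2.0 SD the excess is 0.03-0.05. For an earlier sample (half the shift, residual correlation 0.3) the reading stays within 0.035 of the truth.

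**The case for a change.** The best case for a change is that the protocol itself defines the cases, so this is not detail that can simply be handed to an analysis plan. The label also governs which samples count (5.3, up to diagnosis) and, through 4.4, whether an infant who dies within four weeks is withdrawn and replaced. The word sepsis in the 72-hour sentence is not defined separately, so an investigator could call the infant a case. Counting these infants as cases instead of controls can move the AUC by up to 0.06, more than one standard error. If as many as 10 of 40 true cases were misplaced, power would fall by about 15 points.

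What stands is that the class is implied and not stated. The rest carries less weight. The 0.06 matters only if the written rule is set aside, and counting these infants as cases also brings in contaminated cultures. The 10 of 40 is an assumption: the protocol gives no frequency at all. Holding the infants out, the obvious alternative, is close to a coin toss for accuracy, because removing awkward infants can also flatter a marker.

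The circularity argument shows a larger effect, but only at the diagnostic draw, which weekly sampling from left-over blood does not make typical. It does not arise through NEC, which is graded by Bell stage. The stated aim is new markers, and under 5.3 the immune assays validate proteins that the proteomics has found. Which candidates enter a panel is ordinary analysis-plan content. The list of recorded items in 5.2 is introduced as non-exhaustive and the form itself is not shown, so it cannot be said that these culture results go unrecorded.

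**Conclusion.** No change to the plan is needed. The text makes a culture-positive infant with fewer than two criteria and no NEC a control, and no other passage contradicts that. Wanting laboratory support for a positive culture trades some missed infections against contaminated cultures, and the simulations show no clear gain from reversing the choice.

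Holding these infants out would raise an outside marker's AUC by 0.002-0.025, below the standard error of 0.037-0.044, and would be nearer the truth in 12-13 of 24 settings. These figures rest on assumed infection rates, criterion specificity, marker shifts and culture performance. The true number of such infants is unknown, and the standard error is only a rough yardstick for a bias.

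Analysts would sensibly report how many such infants there are and show CRP and procalcitonin as comparators where diagnostic-draw samples are used. A sentence in 5.1 naming the class would be tidy, but the analysis does not depend on it.

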### 5.2 Information in CRF

All collected data from clinical records will be recorded in the study CRF and feeding CRF by the study investigator at the hospital, including:

- Patient ID number
- Gestational age at birth
- Birth weight and gender
- Type of delivery: C-section or vaginal birth
- Diagnosis of chorioamnionitis:
  - Clinical or histological,
  - Gestational age at diagnosis,
  - Temperature, heart rate, plasma CRP and blood leukocyte counts of mothers at diagnosis
- Diagnosis of LOS and/or NEC:
  - Day of life at diagnosis,
  - Plasma CRP, total leukocyte counts
  - Clinical or culture-proven LOS
  - For culture-proven LOS: identified bacteria
  - Medical or surgical NEC

- Time of blood sampling and volume of blood samples
- Feeding details (in the Feeding CRF)
- Other notes: incidence of RDS, BPD, pneumonia

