## 6 Statistical Plan

### 6.1 Sample Size Determination

Based on the practical issues of admission rate of preterm infants and capacity of temporal blood sampling at the Neonatal Department, we anticipate to include 200 preterm infants (< 32 weeks of gestation) with estimated rate of clinical chorioamnionitis of 15-20% (for overall preterm cases, 40-70% of premature PROM cases), and clinical LOS and/or NEC of 20-30%.

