### 6.2 Statistical Methods

Infant grouping will be categorized based on the defined endpoints to compare: 1. Infants with vs. without chorioamnionitis; 2. Infants with vs. without LOS and/or NEC; 3. Infants with vs. without major mother's own milk feeding. Temporal data obtained from -omic analyses of blood and plasma samples collected every week will be analyzed by multivariate analysis with control for false discovery rates. Other data obtained from immune assays will be analyzed by univariate analysis. A panel of potential biomarkers will be identified by regression algorithm together with ROC analysis.

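### The data list leaves out PROM and perinatal drug exposure, and the validating immune assays are set to univariate analysis although gestational age is collected

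*Protocol*

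**What the plan says.** Protocol section 5.2 introduces its list with "All collected data from clinical records will be recorded in the study CRF and feeding CRF by the study investigator at the hospital, including". The items are gestational age, birth weight, sex, delivery mode, details of the chorioamnionitis and LOS/NEC diagnoses, time and volume of blood samples, and feeding. The list closes with "Other notes: incidence of RDS, BPD, pneumonia". PROM is not among them. Antenatal steroids and antibiotics appear nowhere in the protocol.

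Section 6.1 gives an "estimated rate of clinical chorioamnionitis of 15-20% (for overall preterm cases, 40-70% of premature PROM cases") and puts "clinical LOS and/or NEC of 20-30" per cent. The sample size of 200 is a feasibility figure, with no power calculation behind it.

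Section 6.2 plans three with/without contrasts: chorioamnionitis, LOS and/or NEC, and major mother's own milk feeding. The omic data get a multivariate analysis with false discovery rate control, and the marker panel a regression algorithm with ROC analysis. For the rest, "Other data obtained from immune assays will be analyzed by univariate analysis". Section 5.3 makes the immune assays the step that validates proteins found by proteomics. No covariate, matching or stratification is named for any contrast.

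**The concern.** The groups are observational, so they may differ in more than the condition that defines them. The protocol supplies two such pathways itself. Section 6.1 ties PROM closely to chorioamnionitis. Section 1.1 attributes the high risk of NEC and systemic infection to immaturity, so infants with LOS/NEC can be expected to be less mature than those without.

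If a marker responds to PROM, to a drug given around birth or to immaturity, an unadjusted contrast credits that response to chorioamnionitis or to LOS/NEC. A false discovery rate procedure deals with the number of tests and leaves this bias in place. The validation step gives no protection either: run on the same infants without adjustment, it would tend to confirm a confounded candidate.

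The two gaps differ in kind. The gestational-age part can be dealt with in the analysis, because the data are collected. The PROM, steroid and antibiotic parts need fields that section 5.2 does not list.

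**Working it through.** No stated figure can be reproduced on this point, since the 200 has no alpha, power, effect size or SD behind it. The working sizes the possible bias.

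**Group sizes (section 6.1).** Clinical chorioamnionitis: 200 × 0.15 = 30 to 200 × 0.20 = 40. LOS and/or NEC: 200 × 0.20 = 40 to 200 × 0.30 = 60.

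**False-positive rate under a given bias.** Suppose a marker has no true association and confounding shifts the group means by b SD. For one sample per infant and a two-sided 5% z-test, the statistic is centred at b × √(n₁(200 − n₁)/200), and the rejection rate is Φ(shift − 1.96) + Φ(−shift − 1.96). The values of b are assumptions.

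| Exposed n₁ | √(n₁(200 − n₁)/200) | b = 0.15 | b = 0.30 |
|---|---|---|---|
| 30 | √25.5 = 5.05 | 0.118 | 0.328 |
| 40 | √32 = 5.66 | 0.136 | 0.396 |
| 60 | √42 = 6.48 | 0.163 | 0.494 |

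A bias of 0.15-0.30 SD arises, for example, if an exposure is 30-60 percentage points more common in one group and moves the marker by 0.5 SD (0.30 × 0.5 = 0.15; 0.60 × 0.5 = 0.30).

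**Whether such a gap fits the protocol's own PROM rates.** By Bayes' rule, P(PROM | CA)/P(PROM) = P(CA | PROM)/P(CA). This lies between 0.40/0.20 = 2.0 and 0.70/0.15 = 4.7, whatever the prevalence of PROM. For the absolute gap a prevalence q is needed. The protocol gives none, so 10-20% is assumed.

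- Smallest gap (q = 0.10, P(CA | PROM) = 0.40, P(CA) = 0.20): PROM in 0.10 × 0.40/0.20 = 20% of chorioamnionitis infants and 0.10 × 0.60/0.80 = 7.5% of the others, a gap of 12.5 points.
- Largest gap (q = 0.20, P(CA | PROM) = 0.70, P(CA) = 0.15): 0.20 × 0.70/0.15 = 93% and 0.20 × 0.30/0.85 = 7%, a gap of 86 points.

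The 30-60 point example lies inside this range. If PROM moves a marker by 0.5 SD (assumed), the spurious difference is 0.5 × 0.125 = 0.06 SD to 0.5 × 0.86 = 0.43 SD, and the nominal 5% test is falsely positive in about 6% to 59% of null markers.

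**Gestational age and LOS/NEC.** Assume a gap in gestational age of 0.5-1 SD between the groups and a marker correlation with gestational age of 0.3-0.5. The spurious difference is then 0.5 × 0.3 = 0.15 SD to 1 × 0.5 = 0.5 SD. With 40-60 cases, an unadjusted test is falsely positive in about 14% to 90% of null markers.

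**The case against.** Several stronger readings are tempting, and the protocol does not support them.

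- A reader might infer that marker differences cannot be separated from gestational age. Section 5.2 collects it, with birth weight, sex and delivery mode. The weakness there is in the analysis text only.
- A reader might infer that all contrasts are run without covariates. Only the immune assays are called univariate. A multivariate omic analysis and a panel regression leave room for covariates, and a statistical analysis plan that is not shown may name them. In strict usage, univariate can also mean one marker at a time.
- A reader might infer that the CRF certainly lacks the fields and that the loss is beyond repair. The list in 5.2 is introduced as non-exhaustive, the CRF is an appendix that is not shown, and section 8.2 keeps a key to the coded infants, so later abstraction from hospital records is plausible.

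Three further objections have weight. Section 5.3 limits the analysed samples to those taken up to diagnosis, which largely removes antibiotics given after LOS/NEC is diagnosed; antibiotics given earlier remain. Section 1.1 calls chorioamnionitis the most important risk factor for preterm birth, so gestational age may lie downstream of it, and routine adjustment in that contrast could remove part of a real association. The bias sizes are not from the protocol, and its rates tie only PROM to a study group; for steroids and antibiotics an imbalance is an assumption.

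What remains is the absence of these items from a list that goes down to sample volume and pneumonia, and a stated choice of univariate analysis for the validating assays with no mention of the maturity data already in hand.

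**Conclusion.** The point holds in a limited form. Section 5.2 should list PROM, because section 6.1 makes it a strong correlate of a primary grouping, and should list antenatal steroids and antibiotic exposure alongside it. Section 6.2 should not leave the validating immune assays as a plain univariate comparison when gestational age is collected and the protocol links immaturity to NEC and LOS.

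The size is illustrative: a false-positive rate of about 12-14% at a bias of 0.15 SD and 33-40% at 0.30 SD, for one null marker with 30-40 exposed of 200. These figures assume the bias sizes and one sample per infant. The 30-40 rests on the clinical chorioamnionitis rate, whereas section 5.3 compares clinical/histological cases, whose number is not given. The feeding contrast cannot be sized, because no split is stated. No number in the protocol is wrong on this point. The change is worth making because it is cheap and bears on the primary objective, but the protocol does not show that the results would be invalid without it.

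**What to change.** 1. In section 5.2, add PROM (yes/no and duration), antenatal steroids, and maternal and infant antibiotic exposure with dates, abstracted from existing records. If the CRF already holds these items, say so in 5.2.
2. In section 6.2, replace the univariate analysis of the immune assays with a regression adjusted at least for gestational age in the LOS/NEC and feeding contrasts. For LOS/NEC, add antibiotic exposure before the sample.
3. For the chorioamnionitis contrast, report results both without and with adjustment for gestational age, since it may lie on the causal path. Add a sensitivity analysis with PROM, steroids and antibiotics.

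The cost is minor data abstraction and a few degrees of freedom with about 30-60 cases per contrast, which argues for a short adjustment set. Care and blood sampling are unaffected.

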### **5.3 Sample selection, analysis and comparison**

At the end of the study, the selection of appropriate samples for analysis will be conducted by all investigators of the study. Samples included in the analysis are those collected from birth until the disease diagnosis or completion of 4 postnatal weeks. In case of clinical diagnosis of LOS and/or NEC before completion of 4 weeks, further routine sample collection after diagnosis is continued if feasible.

Temporal samples will be analyzed to perform three separate comparisons:

- Infants without versus with LOS and/or NEC
- Infants without versus with clinical/histological chorioamnionitis
- Infants with major or minor amount of mother's own milk during the first two weeks of life ( $\geq$  or < 50% of feeding times as complete mother's own milk).

Plasma proteomic study will be prioritized and will include as many samples as possible, followed by validation with absolute quantification of potential proteins using immune assays. The type of other -omic analysis for plasma (miRNA profiling) whole blood (transcriptomics or epigenetics) as well as sample size will be decided depending on the results of proteomic study.

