### 4.3 Subject Recruitment and Screening

When infants are admitted to the Neonatal department, parents are informed about this observational study and the possibility to participate by the principal investigator. Signed parenteral consent is required to enter the study. Subjects should be recruited and the first blood sampling will be performed within the first 48 h of life.

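### The LOS/NEC comparison does not relate samples to time of onset, so markers that change only near onset are diluted and the ROC has no prediction window

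*Protocol*

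**What the plan says.** Section 3.2 names as a primary endpoint markers "associated with prognosis and/or diagnosis of neonatal LOS and/or NEC". Prognosis and diagnosis are joined in one endpoint.

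Section 3.1 sorts infants by whether they ever had an episode of LOS and/or NEC. Section 5.3 gives the contrast as "Infants without versus with LOS and/or NEC" and the sample rule as "Samples included in the analysis are those collected from birth until the disease diagnosis or completion of 4 postnatal weeks". Section 6.2 repeats the infant-level grouping, applies multivariate analysis with false-discovery control to the weekly -omic data, and derives a biomarker panel by regression and ROC analysis.

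On timing, Section 3.1 states "Blood sampling is performed every week from birth until 4 weeks of age, or until discharge". Section 4.3 adds that "the first blood sampling will be performed within the first 48 h of life", and Section 5.1 that "LOS is defined as sepsis occurring after 72 hours after birth".

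Section 5.2 has the day of life at diagnosis and the time of each blood sample recorded on the case report form (CRF). No section uses the interval between the two.

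**The concern.** Under the stated grouping, a sample from the first 48 hours of an infant diagnosed in week 4 has the same case status as a sample drawn the day before diagnosis. Analysis by postnatal week does not separate them: within any one week, the case group still mixes infants close to diagnosis with infants weeks away from it.

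A marker that moves only as disease approaches then shows a contrast shrunk by the share of case samples that are not yet near onset. An ROC curve from such data also does not say over what period it predicts, although Section 3.2 asks for prognosis and the Study Summary gives earlier diagnosis as the longer-term aim.

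**Working it through.** **No plan figure to reproduce.** Section 6.1 bases the 200 infants on admission rate and sampling capacity. It gives no effect size, significance level or power.

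**Inputs from the protocol.** N = 200. The LOS/NEC rate is 20–30%, so 40–60 cases; the midpoint, 25%, gives 50 cases and 150 controls. Sampling is weekly, with the first sample within 48 h. LOS starts after 72 h (day 3).

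**Assumptions, not in the protocol.**
- Diagnosis day stands for onset. It is either uniform over days 3–28, or early-peaked: 3 plus a gamma variable with mean 9, truncated at day 28, shape 1, 2 or 3.
- Samples are drawn at a random time in 0–48 h (mean day 1) and on days 7, 14 and 21.
- The marker is shifted 0.8 SD only in samples drawn 7 days or less before diagnosis.
- Tests are two-sided at an unadjusted 5%, with one value per infant.

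**Step 1: longest gap.** Birth sample to diagnosis near day 28: about four weeks.

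**Step 2: share of case samples near onset, uniform onset.**
- Pre-diagnosis samples per case: 1 + 21/25 + 14/25 + 7/25 = 2.68.
- Of these, within 7 days of diagnosis: 5/25 + 3 × 7/25 = 1.04.
- Share: 1.04/2.68 = 39%. By visit it is 20% at 0–48 h, 0.28/0.84 = 33% at day 7 and 0.28/0.56 = 50% at day 14.
- With early-peaked onset (shape 2) the overall share is 51%.

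A separate count used draws on days 1, 7, 14, 21 and 28 and diagnosis on days 4–28. The share within 6 days was 37% (uniform), 57% (early-weighted) and 27% (late-weighted).

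**Step 3: AUC.** Near onset, Φ(0.8/√2) = 0.71. Under the ever/never label, AUC = share × 0.714 + (1 − share) × 0.5. This gives 0.58 at a 39% share and 0.61 at 51%.

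**Step 4: day-7 power.** Noncentral t with noncentrality δ√(n₁n₂/(n₁+n₂)). For ever/never, δ = 0.8 × share. For the 7-day horizon, δ = 0.8, and cases diagnosed later join the comparison group.
- Uniform, ever/never: n₁ = 50 × 0.84 = 42, n₂ = 150, δ = 0.8 × 0.33 = 0.27.
- Uniform, horizon: n₁ = 50 × 0.28 = 14, n₂ = 150 + 28 = 178.

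| Onset | Day-7 share | Ever/never | Power | 7-day horizon | Power |
|---|---|---|---|---|---|
| Uniform | 33% | 42 v 150 | 33% | 14 v 178 | 82% |
| Early, shape 1 | 60% | 31 v 150 | 67% | 19 v 162 | 90% |
| Early, shape 2 | 64% | 39 v 150 | 80% | 25 v 164 | 96% |
| Early, shape 3 | 66% | 42 v 150 | 86% | 28 v 164 | 97% |

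Direct simulation of the uniform row gave 32% and 82%.

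**Step 5: a marker raised throughout.** Suppose eventual cases are shifted 0.5 SD at every sample (uniform onset, day 7). Ever/never (42 v 150) has 81% power. The horizon comparison has 28 future cases among its 178 controls, so δ = 0.5 × (1 − 28/178) = 0.42 and power is about 33%.

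**Step 6: a diagnostic work-up sample.** If each case also contributed one at diagnosis, the uniform share would rise to (1.04 + 1)/(2.68 + 1) = 55%.

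**Step 7: stricter threshold.** At a significance level of 0.001, the uniform day-7 horizon comparison has about 33% power.

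**The case against.** The strongest reply is that aligning samples to onset is detail commonly left to a statistical analysis plan, which is not at hand. The CRF holds both dates, and Section 5.3 lets the investigators select appropriate samples at the end of the study. That stands to this extent: alignment is possible and not ruled out. A reader might infer that the protocol pools all samples under one label regardless of age. The text does not say so; it speaks of weekly temporal data. But the protocol does state a sample rule and a contrast, and neither refers to onset. An open choice made after collection does not fix a window.

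A reader might also infer that early blood from infants who later fall ill is wrongly classed as case material. The documents do not support that: the endpoint includes prognosis, and for a marker raised from birth those samples are valid. Step 5 shows that restricting ever/never to the first sample would lose such markers at later weeks.

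Third, Section 9 describes the blood as left over from routine sampling for screening and diagnosis, so a work-up sample may fall within the window. The text does not guarantee one; if included, it reduces the dilution.

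Finally, this is an exploratory cohort. That lowers the stakes, but exploratory ROC results still need a stated horizon to be interpreted.

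**Conclusion.** The point holds as a mismatch between the stated contrast and the prognosis-and/or-diagnosis endpoint. Dilution of near-onset markers and the missing prediction window follow from Sections 3.1, 5.3 and 6.2.

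The size does not follow from the documents. The gap of 33% against 82% belongs to uniform onset only; with early-peaked onset, ever/never keeps 67–86% power. All these figures assume a 0.8 SD shift confined to the last 7 days. Nor can it be said that near-onset markers will fail the false-discovery cut: the powers are at an unadjusted 5%, and at 0.001 the alternative is itself weak under uniform onset. The change should be made, but as an addition to the ever/never contrast and not a replacement.

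**What to change.** In Sections 5.3 and 6.2:

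- Keep the ever/never contrast at every week and label it the susceptibility analysis.
- Add a prespecified time-to-diagnosis analysis from the CRF day of diagnosis and sampling time. At each weekly sample, among infants still free of LOS/NEC, compare those diagnosed within a stated horizon (for example 7 days) with those who are not. Combine weeks with infant as the cluster.
- Report the AUC for that horizon separately from the diagnostic and ever/never results.

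No new data or sampling are needed. The costs are one more family of tests under false-discovery control and small case groups. With 50 cases and a 7-day horizon there are about 10–14 cases per week if onset is uniform (50 × 0.20 and 50 × 0.28), or about 25 at day 7 falling to 3 at day 21 if it peaks early (shape 2). The added analysis also has less power than ever/never for markers raised from birth, which is why both contrasts are kept.
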